In addition, therapeutic targets for beta-lactam TDM are not well established, with varying practices world-wide [33]. None the beta-lactam targets have been extensively clinically validated. Beta-lactams exhibit time-dependent bactericidal activity and their pharmacokinetic/pharmacodynamics therapeutic target is characterised by the percentage of the dosing interval for which the unbound beta-lactam concentration is maintained above the MIC (fT>MIC). Based on in vitro and in vivo studies, the targets are 40% of the dosing interval (40% fT>MIC) for carbapenems, 50% (50% fT>MIC) for penicillins and 60-70% (60-70%) fT>MIC) for cephalosporins [34-36]. However, clinical observational studies suggest a longer fT>MIC for optimal clinical outcomes (mortality, clinical response, duration of hospital stay) [4,37-39]. In addition, some studies have shown that higher plasma concentrations (fT>4- $5 \times MIC$) may be required for maximal bactericidal activity [40-41], optimal tissue penetration [42-44], optimal clinical response and microbial eradication in patients with pneumonia [45] and

prevention of resistance [6,46]. Centres, that perform beta-lactam TDM, have used the targets 100%fT>MIC, 40-70%fT>4-5xMIC (depending on type of beta-lactam) or 100%fT>4-5xMIC [33] but no studies have compared these targets in terms of clinical outcomes achieved. In this study, we plan to evaluate the correlation between beta-lactam target and clinical outcomes and to determine which beta-lactam target is optimal for clinical practice.

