For all patients, 4 sets of blood samples (5 mL each) will be obtained via venipuncture or existing cannula access within a dosing interval. We propose to obtain 4 samples for each TDM in this study to generate more robust and accurate drug concentration-time curves for calculation of target attainment and to better characterise patients' pharmacokinetic profiles. For most patients (except those on intermittent extracorporeal therapies), blood samples will be obtained during end of infusion, 1 hour after infusion, 2 hours after infusion and within 30 minutes of the next scheduled dose (i.e. trough level) if beta-lactam is given as short infusion over \leq 30 minutes. If beta-lactam is given as extended infusion (e.g. 3-4 hours), blood samples will be obtained at mid-infusion, end of infusion, 1 hour after infusion and within 30 minutes of the next scheduled dose (i.e. trough level). For patients on intermittent extracorporeal therapies (e.g. intermittent dialysis), blood samples will be obtained at end of beta-lactam infusion, at the beginning of dialysis, end of dialysis and within 30 minutes of the next scheduled dose (i.e. trough level).

To ensure therapeutic targets are reached, further blood sampling, according to the schedule above, may be performed after dose adjustments or when there is a change in patient's clinical status (e.g. change in dialysis settings, change in renal function), which may warrant change in beta-lactam dosing regimen. Blood sampling for TDM will be stopped when beta-lactam has been discontinued, when therapeutic targets are achieved or when patient has been discharged from the hospital.

Assay of beta-lactam levels

All blood samples will be sent to our research laboratory for assay via liquid chromatographytandem mass spectrometry. All blood samples will be labelled by our study team using subject codes (no patient identifiers will be used).

Beta-lactam TDM and Dose Individualisation

The treating physicians will have the option to know the results of the TDM, once available. An infectious disease-trained pharmacist may make recommendations on dose adjustments based on the TDM results. However, accepting these recommendations will be at the discretion of the treating physicians.

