The infectious disease trained pharmacist may use pharmacokinetic software to analyse drug concentration-time profile to guide dose adjustments. If available, dose recommendations will be based on the MIC of the known pathogen, which will be provided by the local microbiology laboratory. Where no pathogen was formally identified, MICs are not available or cultures are pending, the highest MIC (according to the Clinical and Laboratory Standards Institute (CLSI criteria) for susceptible bacteria to the antibiotic will be assumed.

Data Collection

All patients will be followed up from study entry to 30 days from study entry, hospital discharge or mortality, whichever occurs earlier.

Data will be collected from electronic medical records, using a standardised data collection form. These will include:

•patient demographics (unique identifier, age, gender, race, body weight, height, comorbidities including Charlson Comorbidity Index)

•pharmacokinetic-specific data (use of extracorporeal therapy/dialysis and settings, urine output, serum creatinine, albumin)

•clinical data (temperature, blood pressure, heart rate, respiratory rate, mortality, cause of mortality, severity of illness indicators such as APACHE II score and SOFA score, incidence of beta-lactam-related adverse events/side effects as reported by primary physicians, admission and discharge date from hospital and from intensive care unit if applicable)

•laboratory data (albumin, serum creatinine, procalcitonin, CRP, total white count)

•infection-related data (site and type of infection, pathogens isolated and their susceptibility results and reported minimum inhibitory concentrations)

•drug-related data (beta-lactam dosing regimens including any change to dosing regimens, concurrent antibiotic use history and their dosing regimens, presence of any drug which may interact with beta-lactams or interfere with beta-lactam assay results)

•beta-lactam assays levels, attainment of therapeutic targets and whether dose adjustments were made

Data will be stored in a password-protected database and only study team members will have access to data. Identifiers will be stored separately from collected data. Data collection forms will not contain identifiers (e.g. NRIC, name, date of birth). All hardcopy data collection forms and consent forms will be stored under lock and key in the cupboard at [name] of

Pharmacy department in Singapore General Hospital.

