8.2. Statistical and Analytical Plans

Our primary outcome will be attainment of beta-lactam therapeutic targets: 100%fT>MIC, 40-70%fT>5xMIC, 100%fT>5xMIC. Proportion of patients, who achieve beta-lactam therapeutic targets, during the first and subsequent TDM will be determined. For the group of patients, who require dose adjustments, after the 1st TDM and need further TDM, the proportion of patients who require dose increment and dose reduction, the number of TDM performed to achieve therapeutic target and the mean/median time required to achieve therapeutic target will also be evaluated.

Correlation of primary outcomes will be made to the following secondary outcomes.

- a. Mortality at the end of therapy and within 30-day mortality.
- b. Days to defervescence
- c. Days to resolution of white blood cell count, pro-calcitonin and C-reactive protein.

Any incidence of adverse effects related to beta-lactam therapy will also be reported and evaluated in correlation to beta-lactam levels.

For univariate analyses with binomial outcomes (e.g. mortality), Chi-square test or Fisher's exact test will be performed where appropriate. For univariate analyses with time-dependent outcomes (e.g. days to defervescence, days to resolution of inflammatory markers), Kaplan-Meier analysis will be performed. For univariate analyses with continuous outcome variables (e.g. APACHE II score, SOFA score), Student's t-test and Mann-Whitney-U test will be performed for parametric and non-parametric data respectively. Multivariate analyses will then be performed to include potential confounders such as APACHE II score, SOFA score, Charlson comorbidity index, use of beta-lactam as culture-directed therapy, presence of multi-drug resistant infection, and presence of concurrent infections requiring additional antibiotics. Logistic regression will be used for binomial outcomes (mortality) while Cox regression will be used for time-dependent outcomes (days to defervescence, days to resolution of inflammatory markers).

To evaluate population pharmacokinetics in various patient groups, a specialised pharmacokinetic software will be used to develop population pharmacokinetic models. Model simulation will then be performed to design empiric dosing recommendations to guide local practice.

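### Intermittent-dialysis sampling puts only two levels on the pre-dialysis decline and can duplicate the last level when the next dose closely follows dialysis, so 40-70%fT>5xMIC may be overstated

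*Combined protocol and SAP*

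**What the plan says.** Section 5 (Blood sampling) gives intermittent-dialysis patients four samples: "at end of beta-lactam infusion, at the beginning of dialysis, end of dialysis and within 30 minutes of the next scheduled dose". It does not say how dose and dialysis are timed relative to each other. It offers no substitute time if the third and fourth samples coincide.

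For other patients on short infusions the rule reads "blood samples will be obtained during end of infusion, 1 hour after infusion, 2 hours after infusion and within 30 minutes of the next scheduled"; the last of these four is the trough. They therefore have two fixed samples in the first two hours after the peak. Dialysis patients have none at a fixed time between the end of infusion and the start of dialysis.

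The stated purpose of four samples is "to generate more robust and accurate drug concentration-time curves for calculation of target attainment". Section 8.2 then defines the endpoint: "Our primary outcome will be attainment of beta-lactam therapeutic targets: 100%fT>MIC, 40-70%fT>5xMIC, 100%fT>5xMIC". The class values behind the 40-70% range are in section 1: "the targets are 40% of the dosing interval (40% fT>MIC) for carbapenems, 50% (50% fT>MIC) for penicillins", and 60-70% for cephalosporins.

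On turning levels into time above target, section 5 says only that the pharmacist "may use pharmacokinetic software to analyse drug concentration-time profile to guide dose adjustments". Section 8.2 describes population modelling separately and does not say that it produces the primary outcome.

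**The concern.** If the next dose is due as dialysis ends, the end-of-dialysis sample and the trough measure the same level. One of the four assays then adds almost nothing, in a study whose size is set by its assay budget.

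Meanwhile the decline before dialysis, which is most of a 24 or 48 h interval if dialysis comes at its end, is fixed by two levels. One is the end-of-infusion peak, which may be drawn while drug is still distributing. A straight line on the log scale from such a peak to the pre-dialysis level runs above the true curve, and the 40-70% points of the interval lie on that stretch. A dialysis patient who misses 40-70%fT>5xMIC could be scored as attaining it. Because section 5 stops TDM sampling once targets are reached, a false attainment could also end that patient's sampling. The same profiles feed the dialysis pharmacokinetics in secondary objective 2.

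**Working it through.** **1. The plan's own figure.** 40,000 / 125 = 320 assays and 320 / 4 = 80 patients (section 8.1). Both reproduce, and neither is in dispute. A four-sample TDM costs 4 × $125 = $500, of which $125 buys the near-duplicate when the last two samples coincide.

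**2. When the samples coincide.** Let g be the hours from end of dialysis to the next dose. The trough is drawn in the last 0.5 h before the dose, so the two samples are between max(0, g − 0.5) and g hours apart. They can coincide only if g ≤ 0.5 h. At g = 4 h they are 3.5 to 4 h apart.

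**3. Worked examples.** The documents give no pharmacokinetic values, so those below are assumptions. With the end-of-infusion level set to 100 at time 0, let C(t) = 100[f·2^(−t/h1) + (1 − f)·2^(−t/h2)]. Here f is the fast-phase share, h1 the fast half-life and h2 the terminal half-life. Take 20 h off dialysis plus 4 h of dialysis ending at the next dose (24 h interval), f = 0.5 and h1 = 0.5 h.

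- *h2 = 10 h, threshold 20.* True crossing: 10·log2(50/20) = 13.2 h, or 55.1% of the interval. Pre-dialysis level: 50·2^(−2) = 12.5. The log-linear line falls three halvings in 20 h (6.67 h each) and reaches 20 at 6.67·log2(5) = 15.5 h, or 64.5%. A 60% cut-off is passed wrongly.
- *h2 = 20 h, threshold 40.* True crossing: 20·log2(50/40) = 6.4 h, or 26.8%. Pre-dialysis level: 25. The line falls two halvings in 20 h and reaches 40 at 10·log2(2.5) = 13.2 h, or 55.1%. Cut-offs of 40% and 50% are passed wrongly.
- *f = 0.* The line is the true curve, so the error is zero.
- *First example with a sample at 2 h.* The level there is 100(0.5·2^(−4) + 0.5·2^(−0.2)) = 46.7. Joining 46.7 at 2 h to 12.5 at 20 h gives a crossing at 13.6 h, or 56.6% against the true 55.1%.

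**4. Grid.** The same model with 8, 20 or 44 h off dialysis, h2 of 6, 10 or 20 h and thresholds of 10, 20 or 40 gives 27 scenarios for each f and each h1 (0.25, 0.5 or 1 h). Dialysis lasts 4 h at four times the terminal rate, with samples 3 and 4 merged.

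| f | Log-linear overstatement (points) | Scenarios over 1 point |
|---|---|---|
| 0 | 0 | 0 of 27 |
| 0.3 | 0 to 11.0 | 15 of 27 |
| 0.5 | 0 to 28.3 | 17 of 27 |

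The error was never negative. It was zero whenever the threshold was first crossed during dialysis or not at all. No scenario misclassified a 100% target. Joining the levels linearly overstated by up to 44.8 points even at f = 0. At f = 0.5, adding a 2 h sample cut the largest log-linear error from 28.3 to 0.4 points (h1 = 0.25 h), from 28.2 to 5.3 (0.5 h) and from 26.9 to 14.2 (1 h).

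**5. Two-compartment model at steady state.** Assumed: 0.5 h infusion, distribution half-life 0.3-0.5 h, off-dialysis half-life 6-15 h, central volume 0.5-0.7 of steady-state volume, 4 h dialysis raising clearance 3- to 6-fold, log-linear joining.

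| True fT, 24 h interval | Scored, next dose at end of dialysis | Scored, next dose 4 h later |
|---|---|---|
| 30% | 35-49% | 35-45% |
| 40% | 44-56% | 43-51% |
| 60% | 62-68% | not needed here |
| 70% | 71-75% | not needed here |

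At 48 h with overlap, 30% is scored 33-44% and 40% is scored 43-52%. With distinct samples, 30% is scored 33-43%. In the overlap case, a sample 1.5 h after infusion cuts the error to at most about 5 points.

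The last column of the table shows that most of the error remains when all four times are distinct. It comes from having two pre-dialysis levels, not from the overlap.

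**The case against.** The strongest reply is that the overlap is not the cause. Every intermittent-dialysis patient has only two levels before dialysis, and step 5 shows similar errors without any overlap. That stands. A reader might infer that the duplicate sample produces the bias, or that patients with well-separated dose and dialysis are safe; neither is so.

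A reader might also infer that a sample is lost whenever a dose follows dialysis. The documents do not support that: the samples merge only at a gap of about 30 minutes or less, and dose timing is not stated.

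Nor do the documents show that time above 5xMIC is overstated as a matter of course. No passage prescribes log-linear joining. Software is allowed for individual profiles, and a model with informative priors would shrink the error. The error is also much smaller near the 60-70% cephalosporin values than at 30-40%, and two of the three primary targets depend on the lowest level, which is measured. Dialysis is one of several indications with no stated number, so no effect on the overall primary proportion can be shown.

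Finally, the pre- and post-dialysis samples have a purpose: they show drug removal by dialysis, a question that section 1 raises. The proposed change keeps both.

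What the reply does not answer is that the rule, followed as written, spends an assay on a near-duplicate when the two late samples coincide, and that the plan names no calculation method that would protect against the error.

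**Conclusion.** The point holds in limited form. For intermittent dialysis the rule places two levels on the whole pre-dialysis decline. When the next dose is due within about 30 minutes of the end of dialysis, it yields three distinct times from four assays. The overlap matters because it frees a sample, not because it creates the gap.

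The 40-70%fT>5xMIC target may then be overstated, provided that decline is two-phase, levels are joined log-linearly and 5xMIC is crossed before dialysis. At a 24 h interval the assumed parameters give roughly 5 to 19 points at a true 30% (35 − 30; 49 − 30), falling to 1 to 5 points at a true 70% (71 − 70; 75 − 70). Under log-linear joining the error is zero for a one-phase decline. The 100%fT>MIC and 100%fT>5xMIC targets are not materially affected, although rebound after dialysis was not modelled in the grid. All sizes rest on assumed pharmacokinetics, and the number of patients concerned cannot be derived from the documents.

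**What to change.** Add one sentence to the dialysis sampling rule in section 5: if the next dose is due within 30 minutes of the end of dialysis, one sample serves as both the end-of-dialysis level and the trough, and the freed sample is drawn 1-2 hours after the end of infusion, as already done for other short-infusion patients. The choice has to be made from the planned schedule at the time of the infusion, because the early sample comes first.

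Samples and assays per TDM stay at four. What is lost is a duplicate level at the end of the interval. Patients whose dose and dialysis are well separated keep the sparse pre-dialysis sampling, and this should be acknowledged when their 40-70%fT>5xMIC is reported. A line in section 8.2 on how time above target is calculated would let readers judge how far the error applies.

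The change moves a study sample only. It does not concern dose or dialysis timing.

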6. SAFETY MEASUREMENTS

6.1. Definitions

Serious adverse event (SAE) in relation to human biomedical research, means any untoward medical occurrence as a result of any human biomedical research which:

- results in or contributes to death
- is life-threatening
- requires in-patient hospitalisation or prolongation of existing hospitalisation
- results in or contributes to persistent or significant disability/incapacity or
- results in or contributes to a congenital anomaly/birth defect
- results in such other events as may be prescribed

Adverse event (AE) in relation to human biomedical research means any untoward medical occurrence as a result of any human biomedical research which is NOT serious. Adverse event can be any unfavourable and unintended sign (including an abnormal laboratory finding), symptom, or disease possibly/ probably/ definitely associated with the participant in the human biomedical research.

6.2. Collecting, Recording and Reporting of Adverse Events and Serious Adverse Events to CIRB

Reporting of adverse events involves the Principal Investigator submitting to CIRB the SAE Reporting Form to CIRB within the stipulated timeframe. The Principal Investigator is responsible for informing the institution representative, the chairman medical board (when required by the institution for local SAE resulting in death), sponsor or regulatory bodies as required and appropriate.

Reporting timeline to CIRB:

- Local unexpected SAE resulting in death that are related events should be reported immediately within 24 hours of the Principal Investigator becoming aware of the event.
- Local unexpected, life-threatening SAE that are related events should be reported as soon as possible but no later than 7 calendar days after the Principal Investigator is aware of the event, followed by a full report within 8 additional calendar days.
- Local unexpected, not life-threatening SAE that are related events, should be reported no later than 15 calendar days after the Principal Investigator is aware of the event.
- An increase in the rate of occurrence of Local expected SAE that are related events,

which is judged to be clinically important, should be reported within 15 calendar days after the Principal Investigator is aware of the event.

- Local unexpected AE that are related events should be reported at least annually (together with Study Status Report for annual review).
- Non-local unexpected SAE that are fatal or life threatening and related should be reported not later than 30 calendar days after the Principal Investigator is aware of the event.

6.3. Safety Monitoring Plan

This is an observational study; hence no clinical safety monitoring is required.

6.4. Complaint Handling

As stated in the informed consent form, patients can complain to the site PI or CIRB. If CIRB receives any complaints, CIRB will inform the site PI.

7. DATA ANALYSIS

7.1. Data Quality Assurance

The quality and accuracy of the data collected will be reviewed once every 3 months by the investigators.

A standardised data collection form will be used. All investigators need to have a good understanding on how to fill up the form accurately. The transcribing of the information from the data collection form to the electronic database will also be reviewed and checked regularly by the investigators.

7.2. Data Entry and Storage

Data will be stored in a password-protected electronic database and only study team members will have access to data. Identifiers will be stored separately from collected data. Data collection forms will not contain identifiers (e.g. NRIC, name, date of birth). All hardcopy data collection forms and consent forms will be stored under lock and key in the cupboard at [name] of Pharmacy department in Singapore General Hospital. Only the PI and designated study members have access to the locked cupboard.

Based on SingHealth Cluster Research Data Management Policy – Clinical Trial and Clinical Research, research data will be retained in a secured storage facility (mentioned in section R1(i) for a minimum of 7 years after completion of research study or date of publication of the research using the research data, whichever is later. The data collected will be also stored and used for future research.

8. SAMPLE SIZE AND STATISTICAL METHODS

8.1. Determination of Sample Size

Patients will be recruited until 320 assays are performed (based on budget of \$40,000, estimated cost of each assay is \$125, number of assays = 40,000/125 = 320 assays). This will be roughly equivalent to 80 patients, assuming patients will have 4 assays each.

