To address the gaps in evidence above, we propose a prospective observational study to evaluate the feasibility of beta-lactam TDM in the local setting. Our target population will be adult patients (21 years old and above), admitted to Singapore General Hospital, are receiving beta-lactams for documented or suspected infection and belong to the following group of patients who will most benefit from beta-lactam TDM: i.e. critically ill patients (admitted to intensive care units, intensive care areas, high dependency wards), haematology/oncology patients, burns patients, patients with extracorporeal therapies which will alter beta-lactam pharmacokinetics (e.g. extracorporeal membrane oxygenation, dialysis), patients with resistant infections or deep-seated infections requiring high dose beta-lactam therapy and patients, who are suspected or at risk of developing beta-lactam adverse effects. We will prospectively collect four blood samples over a dosing interval from each patient. The beta-lactam levels will be assayed using liquid chromatography with tandem mass spectrometry. Attending physicians will have the option of knowing the results and whether to accept dose adjustments recommendations by trained infectious disease pharmacist. Proportion of patients attaining therapeutic targets during the first and subsequent TDM will be evaluated. Patients will also be followed up for clinical outcomes such as mortality and clinical response.

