2. HYPOTHESIS AND OBJECTIVES

We hypothesise that current licensed beta-lactam dosing regimens are suboptimal in at least half our patients: patients with severe sepsis in intensive care units/high dependency wards, burns patients, patients requiring dialysis and other forms of extracorporeal therapy, haematology/oncology patients, and patients with resistant pathogens or deep-seated infections requiring high dose beta-lactam therapy. Hence, beta-lactam TDM would be necessary for these patients to optimise their dosing regimens and improve their clinical outcomes.

Our primary objective is to evaluate proportion of sub-optimal beta-lactam levels in correlation to MIC and the need for dose adjustments

Our secondary objectives include:

- 1. Correlating the achieved pharmacokinetic/pharmacodynamic therapeutic targets (100%T>MIC, 40-70%T>5xMIC, 100%T>5xMIC) with clinical outcomes (mortality, clinical response, microbial eradication) in the different sub-groups mentioned above
- 2. Characterising beta-lactam pharmacokinetics (as exploratory analysis) for certain patient populations, with limited beta-lactam pharmacokinetics characterised in primary literature (e.g. those requiring extracorporeal therapy, various types of dialysis), to aid design of empiric dosing regimens suitable for local practice.

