5. STUDY DESIGN AND PROCEDURES/METHODOLOGY

This is a prospective observational study conducted in Singapore General Hospital from October 2019 to September 2020. Patients will be screened for eligibility using criteria 4.3 and 4.4. If women of childbearing age are eligible, the beta HCG result taken during the potential subject's course of hospitalisation will be used to exclude pregnant women. If no beta HCG result is available, clinical case notes will be referred to confirm non-pregnancy status.

Eligible patients will be approached by their treating physicians to seek their consent to be referred to the study team. Informed consent will be taken directly from the patient by the study team once patient is agreeable to be referred to the study team. For subjects who do not have the mental capacity to exercise rational judgement, primary physician will assess and document their mental capacity using the Documentation of Capacity form and substituted consent will be obtained by the study team from the spouse, parent, guardian, or legally acceptable representative of the subject. Consent for continued participation will be obtained from patient directly when he regains mental capacity to give informed consent.

Blood sampling and data collection will only commence once informed consent has been taken. Subjects may withdraw voluntarily from participation in the study at any time. Once they have withdrawn from the study, all subsequent blood sampling and data collection will be discontinued.

All patients will be followed up until end of beta-lactam therapy, 30 days from commencement of beta-lactam therapy, hospital discharge or mortality, whichever occurs later.

Blood sampling:

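### The figure of roughly 80 patients allows for one complete TDM each and no repeats, although repeat four-sample TDMs are permitted, analysed and given no separate assay allowance

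*Combined protocol and SAP*

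**What the plan says.** Section 8.1, repeated in section 4.1, derives the study size from money: a budget of $40,000 at $125 per assay gives 320 assays, and recruitment continues until that many have been run. The patient number follows: "This will be roughly equivalent to 80 patients, assuming patients will have 4 assays each".

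Section 5 defines what an assay count means for one patient. Under blood sampling: "We propose to obtain 4 samples for each TDM in this study". Under assay of levels: "All blood samples will be sent to our research laboratory for assay". The same section provides for repeats: "further blood sampling, according to the schedule above, may be performed after dose adjustments". It allows them also when the patient's clinical status changes, and it sets no maximum number of TDMs.

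The repeats are part of the analysis. Section 1 announces: "Proportion of patients attaining therapeutic targets during the first and subsequent TDM will be evaluated". Section 8.2 says the same and adds, for patients who need a dose adjustment and further TDM, the number of TDMs and the time taken to reach target.

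Two provisions in section 5 can leave a set incomplete. On withdrawal: "Once they have withdrawn from the study, all subsequent blood sampling and data collection will be discontinued". On the end of treatment: "Blood sampling for TDM will be stopped when beta-lactam has been discontinued"; discharge also ends sampling.

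**The concern.** Four assays per patient is one complete TDM and nothing more. The only patient number in the plan therefore assumes that no patient has a repeat, while the analysis section expects some will. With complete sets, the two cannot both hold. Either there are 80 patients and no data for the analyses of subsequent TDMs, or there are repeats and fewer than 80 patients.

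This matters because recruitment stops on assays while the conclusions rest on patients. The primary target-attainment proportions, the subgroup correlations in section 2 and the adjusted mortality and time-to-event models in section 8.2 all depend on how many patients are enrolled. A reader who takes 80 as the expected size may overestimate their precision.

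**Working it through.** **Inputs.** Budget $40,000, cost $125 per assay and 4 assays per patient (sections 4.1 and 8.1); 4 samples per TDM, all assayed (section 5). The documents give neither the number of repeat sets per patient nor the completeness of sets, so both are varied below as assumptions.

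**The plan's own figure.** 40,000/125 = 320 assays; 320/4 = 80 patients. The arithmetic is correct.

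**What 320 assays buy.** With complete sets, 320/4 = 80 TDM sets, first and repeat together. Hence patients + repeat sets = 80, and each repeat set removes one patient.

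**General form.** Let m be the mean number of assays per set and r the mean number of repeat sets per patient. Then N = 320/[m(1 + r)].

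| r (assumed) | N at m = 4 | N at m = 3.75 | N at m = 3.5 |
|---|---|---|---|
| 0 | 80.0 | 85.3 | 91.4 |
| 0.10 | 72.7 | 77.6 | 83.1 |
| 0.50 | 53.3 | 56.9 | 61.0 |
| 1.0 | 40.0 | 42.7 | 45.7 |

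For example, at m = 4 and r = 0.50: 320/(4 × 1.5) = 53.3.

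**Break-even for 80 patients.** Setting N = 80 gives r = 4/m − 1.
- m = 4: r = 0.
- m = 3.75: r = 0.067, or 80 × 0.067, about 5 repeat sets in the whole study.
- m = 3.5: r = 0.143, or about 11 repeat sets.

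Turned round, m = 4/(1 + r). To keep 80 patients, the mean set would have to shrink to 3.64 assays at r = 0.10, 2.67 at r = 0.50 and 2.00 at r = 1.0.

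**Precision.** Section 2 hypothesises that "current licensed beta-lactam dosing regimens are suboptimal in at least half our patients", so 50% is a natural reference proportion. The 95% half-width is 1.96 × √(0.25/N), taken at whole numbers of patients.

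| N | Half-width (percentage points) |
|---|---|
| 80 | 11.0 |
| 73 | 11.5 |
| 61 | 12.5 |
| 53 | 13.5 |
| 40 | 15.5 |

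**The case against.** The best defence is that this is a disclosed approximation. The sentence says the figure is rough and states its assumption, and the operative rule is the assay count. If repeats occur, recruitment simply ends with fewer patients, and nothing in the protocol is breached. Repeats are also optional: section 5 permits but does not require them, treating physicians may decline dose recommendations, and sampling stops once targets are reached. The hypothesis that at least half of patients are underserved by licensed dosing is therefore not a repeat rate. Nor do the documents say in words that repeats are charged to the same 320 assays. Finally, incomplete sets push the other way: at m = 3.5 and r = 0.10 the projection is about 83 patients, above the stated 80.

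Much of this stands. The eighty is a projection and not an enrolment target. The repeat rate is unknown, and a shortfall is not certain. The single pool is an inference, though a firm one: the stopping rule counts assays without distinguishing first from repeat, and only one budget is given. The assumption in section 8.1 does not itself prevent repeat sampling, so repeat data will exist if repeats are done; the conflict is in the projected number.

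The conflict nevertheless remains. Stating an assumption does not reconcile it with sections 5 and 8.2, which plan for the event it excludes. A fall from 80 to 53 is a loss of 27/80, about a third, which is more than a rough figure covers. Incomplete sets would have to be severe to absorb moderate repeat rates, averaging 2.67 assays instead of four at r = 0.50.

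**Conclusion.** The concern holds. The arithmetic is right, but with complete sets 80 patients is reached only if no TDM is repeated, and the plan intends to analyse repeats. Under assumed rates of 0.10 to 1.0 repeat sets per patient, complete sets give about 73 down to 40 patients, with half-widths for a 50% proportion of 11.5 to 15.5 points against 11.0 at 80.

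This rests on two readings: one sample is one assay, as section 5 indicates, and repeats draw on the same 320 assays, as the stopping rule implies. The size of any shortfall cannot be fixed from the documents, and a low repeat rate combined with incomplete sets could cancel it. Since the plan sets no power or precision target, no calculation has failed; the stated patient number is unsupported. It should be corrected.

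**What to change.** In sections 4.1 and 8.1, replace the sentence giving 80 patients with wording such as:

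> The 320 assays correspond to 80 complete four-sample TDMs in total, first and repeat together. This is about 80 patients only if no TDM is repeated, and one patient fewer for each complete repeat TDM (for example, about 53 patients if half have one repeat, an assumed rate). Incomplete sample sets would offset this in part. For a proportion of 50%, the 95% confidence half-width is about 11.0 percentage points with 80 patients and 13.5 with 53.

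The 320-assay stopping rule and the repeat sampling in section 5 stay as they are. The cost is wording in two places, with no additional patients, assays or budget. The only drawback is that the stated size may read less favourably.
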